8.4.6 Concomitant Therapy

The number of patients taking Vitamin D and Calcium Therapy during the treatment and follow-up periods will be summarised by treatment and overall.

In addition the number of patients taking Zoledronic Acid Therapy at Month 12, Month 18 and not at all during the follow-up period will be summarised by site, treatment and overall.

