Variables will be analysed according to their scale using general methods as described above. Results will be presented overall and by initial treatment assignment. In addition, subgroup analyses will be performed for HRpQCT, DXA, vertebral radiograph, CTX-1 and P1NP based on the administration of zoledronic acid during the follow-up phase (none; at Month 12; at Month 18). Also, the frequency of administration of zoledronic acid during the follow-up phase will be related both to the site and to the 12 months outcome for both primary efficacy endpoints.

HRpQCT Validation Analysis

Validation analyses to the HRpQCT measurements will be described in a separate analysis plan.

2. Schedule of Activities (SoA) Treatment Period

Procedure	Screening (up to 28 days before Day 1)	Months													Notes All visits ± 4 days.	
		Base-line	1	2	3	4	5	6	7	8	9	10	11	EOT/12		
COL1A1/COL1A2 Mutation confirmation	X															If not available, consent can be obtained and test conducted prior to main study screening
Informed consent	X															Main study consent and bone biopsy
Inclusion and exclusion criteria	X															Re-confirm at Baseline
Demography	X															
Full physical examination including height and weight	X							X							X	
Brief physical examination		X	X	X	X	X	X		X	X	X	X	X			
Past and current medical conditions	X															
Prior medications	X															In the last 2 years

Procedure	Screening (up to 28 days before Day 1)	Months													Notes All visits ± 4 days.	
		Base-line	1	2	3	4	5	6	7	8	9	10	11	EOT/12		
Serum pregnancy test (WOCBP only)	X															
Urine pregnancy tests (WOCBP)		X	X	X	X	X	X	X	X	X	X	X	X	X	X	
Safety Laboratory assessments	X	X	X	X	X			X			X			X	To be collected pre-dose	
25-OH-Vitamin D	X	X	X		X			X			X			X		
12-lead ECG	X							X						X		
Vital signs	X	X	X	X	X	X	X	X	X	X	X	X	X	X		
Randomisation		X														
Study treatment		X	X	X	X	X	X	X	X	X	X	X	X		Weight will be measured to calculate dose	
HRpQCT	X				X			X						X	M6 and M12 scans be conducted ±7days of visit M3 for open-label participants only	
DXA	X							X						X	Calcium tablets should not be taken 2 hours prior to DXA lumbar scan	

Procedure	Screening (up to 28 days before Day 1)	Months													Notes All visits ± 4 days.	
		Base- line	1	2	3	4	5	6	7	8	9	10	11	EOT/ 12		
Vertebral Radiograph	X							X							X	
Fracture Assessment & Radiograph		←-----→													Radiographs will be taken in the event of a symptomatic fracture	

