8.1.1. Zoledronic acid therapy

Following the end of setrusumab therapy all participants will have the option to receive a dose of zoledronic acid at 12 and 18 months. This will be prescribed at the discretion of the treating physician and in line with local guidelines.

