11.3.4. Follow-Up Period Analyses

Variables will be analysed according to their scale using general methods as described above. Results will be presented overall and by initial treatment assignment. In addition, subgroup analyses will be performed for HRpQCT, DXA, vertebral radiograph, CTX-1, and P1NP based on the administration of zoledronic acid during the follow-up period (none; at Month 12; at Month 18). Also, the frequency of administration of zoledronic acid during the follow-up period will be related both to the site and to the 12 months outcome for both primary efficacy endpoints.

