8.5.1 Analysis methods

For all continuous outcomes, where appropriate, an ANCOVA model analysis will be performed. Analyses will include the fixed, categorical effects of treatment and randomisation stratum as well as the associated baseline value as a covariate. Significance tests for treatment differences (between Setrusumab doses) will be based on least-squares means (LSMeans).

ANCOVA analyses dealing with nested observations within a patient (e.g., vertebral assessments) will consider this relationship in the modelling by specifying patient as a random factor.

If the input data is log-transformed then LSMean and LSMeans differences between treatment groups will be back-transformed to their original scale for descriptive purposes. After subtracting the geometric mean of the log baseline values, the back-transformed LSMeans will correspond to the percentage change from baseline, while the back-transformed LSMeans differences will correspond to the ratio of percentage changes from baseline.

Time to event variables (e.g., time to first fracture) will be analysed using Kaplan-Meier methods, and quartiles for the median time to event will be presented together with their 95% confidence intervals.

Count variables (e.g number of new fractures) will be analysed using Poisson regression. Analyses will include treatment and randomisation as fixed effects and the logarithm of the duration of exposure to study medication will be included as an offset variable in the model. In case over dispersion is a concern, the negative-binomial regression model will be applied instead.

For binary outcomes the proportion of patients with a response will be summarised and compared between treatment groups using Chi squared test.

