8.5.4.5 Follow-up Period Subgroup Analysis

A subgroup analysis (descriptive statistics and associated ANCOVA analyses) will be performed for HRpQCT, DXA, vertebral radiograph, CTX-1, and P1NP parameters at all follow-up visits by the administration of zoledronic acid during the follow-up period (none; at Month 12; at Month 18).

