8.7.4 Follow-up Analysis

The data collected during the off treatment follow-up will be separately analysed and published in an addendum to the CSR.

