9 CHANGES TO PLANNED ANALYSIS FROM PROTOCOL

Not applicable.

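### The SAP drops, without declaring it, the protocol's analysis relating follow-up zoledronic acid use to the Month 12 outcome of both primary endpoints

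*SAP*

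**What the plan says.** Zoledronic acid is optional at Months 12 and 18. Protocol section 8.1.1 states: "This will be prescribed at the discretion of the treating physician and in line with local guidelines". Who receives it is therefore not randomised.

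For follow-up, the protocol sets two tasks that involve the drug. One is subgroup analyses by zoledronic acid use. The other concerns who was given it: under Protocol section 11.3.4 the frequency of use "will be related both to the site and to the 12 months outcome for both primary efficacy endpoints". The synopsis, under Follow-Up Period Analyses, has the same requirement: "the frequency of administration of zoledronic acid during the follow-up phase will be related both to the site and to the 12 months" outcome of the two primary endpoints.

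The SAP covers the drug in two places. Section 8.4.6 counts participants given it at Month 12, at Month 18 and "not at all during the follow-up period will be summarised by site, treatment and overall". Section 8.5.4.5 plans descriptive statistics and ANCOVAs at the follow-up visits "by the administration of zoledronic acid during the follow-up period (none; at Month 12; at Month 18"). On methods for the follow-up period, section 8.7.4 adds only this: "The data collected during the off treatment follow-up will be separately analysed and published in an addendum to the CSR". Section 9, on changes from the protocol, reads "Not applicable".

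**The concern.** Participants given zoledronic acid at Month 12, at Month 18 or not at all are groups formed by clinical decision after a year of setrusumab. If those decisions tracked how well a participant had responded by Month 12, the groups already differed before zoledronic acid could act. Part of any difference seen at Months 18 and 24 would then be carried over from Month 12.

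The protocol provided for this by asking that use be set against the Month 12 outcome. Without that output, a reader of the subgroup tables in the follow-up report cannot tell a zoledronic acid effect from better or worse responders having received the drug. Adjusting for baseline does not help, because response to setrusumab accrues after baseline.

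**Working it through.** The point is an omitted analysis, and the plan states no figure to reproduce. The check is to set the protocol's requirements beside the SAP and then test the possible explanations.

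| Protocol synopsis and 11.3.4 | SAP |
|---|---|
| Subgroup analyses by zoledronic acid use | Present, 8.5.4.5 |
| Use related to site | Present as counts, 8.4.6 |
| Use related to Month 12 radius Tr. vBMD | Absent |
| Use related to Month 12 FEA bone strength | Absent |

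**Is it supplied by the general methods?** SAP section 8.5.1 says of the ANCOVA: "Analyses will include the fixed, categorical effects of treatment and randomisation stratum as well as the associated baseline value as a covariate". Its tests are between setrusumab doses. No model there has zoledronic acid use as a response or as a term, and none has a Month 12 value as a predictor.

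**Is it deferred to another plan?** The SAP introduction sends only HRpQCT validation and the PK analyses elsewhere. Section 8.7.4 names a report addendum and no further analysis plan.

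**Is it a version difference?** The SAP cites protocol Amendment 5, dated 12 December 2018. Protocol Appendix 9 describes that as the amendment that added optional zoledronic acid. The Amendment 6 change list shows no edit to section 11.3.4.

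**Is it a declared change?** No. SAP section 9 declares none.

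**How large could the selection be?** The documents give neither the Month 12 difference between users and non-users nor the correlation between visits, so only a range of assumptions is possible. With equal SDs at both visits and no zoledronic acid effect, the carried-over Month 18 difference is the correlation times the Month 12 difference:

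- correlation 0.3, Month 12 difference 0.25 SD: 0.3 × 0.25 = 0.075 SD
- correlation 0.8, Month 12 difference 0.5 SD: 0.8 × 0.5 = 0.40 SD
- correlation 0.9, Month 12 difference 0.75 SD: 0.9 × 0.75 = 0.675 SD

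These are unadjusted and purely illustrative. They run from negligible to substantial, which is why the data should be looked at. The omission does not depend on them.

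**The case against.** The omission itself cannot be argued away, but several stronger inferences are tempting and the documents do not support them.

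- A reader might infer that selection into the zoledronic acid groups is not examined at all. The by-site counts survive, the SAP adds counts by treatment, and section 8.1.8 lists individual data for all randomised patients. What is missing is the Month 12 outcome.
- A reader might infer that the whole question of treatment offset rests on non-randomised groups. Protocol section 11.3.4 presents follow-up results overall and by initial assignment, with the zoledronic acid subgroups as an addition. SAP section 8.5.3.5 analyses its listed HRpQCT parameters through follow-up in the same way as the primary endpoint, with treatment as the factor. Zoledronic acid use can still blur offset within an arm.
- A reader might want the Month 12 value added to the ANCOVA in SAP section 8.5.4.5. Read with section 8.5.1, that section most naturally means dose comparisons within each zoledronic acid category; no test between categories is defined. Month 12 response is itself an outcome of dose, so putting it in the dose model would adjust away the dose effect.
- A reader might measure the illustrative carry-over against the change the trial is powered to detect. That is a within-arm change from baseline, and is no yardstick for a difference between zoledronic acid groups.

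Two further objections stand in part. The documents do not say that treating physicians see Month 12 Tr. vBMD or FEA results when prescribing: images are centrally read and investigators are blinded to dose in the blinded arms. Selection through other information, such as DXA or the turnover markers tested locally in follow-up, is possible but not documented. Also, the subgroup analysis is exploratory and reported in an addendum, so the consequence is limited.

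**Conclusion.** The point holds as a discrepancy between protocol and SAP with a limited but real consequence. Of the two relations the protocol requires, site is kept and Month 12 outcome is missing for both primary endpoints. The statement in SAP section 9 is therefore incorrect. Because prescribing is discretionary, the subgroup results in section 8.5.4.5 cannot be checked for selection on Month 12 response.

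This conclusion rests on the text alone. Whether selection occurred, and in which direction, is unknown; the requested table would show how far the groups differed at Month 12. The primary Month 12 test, its type I error and the sample size are untouched. It should be corrected before the follow-up analysis is run.

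**What to change.** In SAP section 8.4.6 or 8.5.4.5, restore the protocol analysis. Summarise Month 12 change from baseline in radius Tr. vBMD and in FEA bone strength by zoledronic acid category (none; Month 12; Month 18), overall and by treatment where numbers allow. State which category holds a participant dosed at both times, since the present labels do not. Correct section 9; if the sponsor prefers not to do the analysis, declare and justify the omission there.

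If follow-up results are to be compared between zoledronic acid categories, define that comparison explicitly, adjust it for the Month 12 value, and label it non-randomised. Leave the setrusumab dose comparison without that covariate. Month 12 adjustment cannot account for Month 18 decisions based on later information, and the text should say so.

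The cost is SAP wording and one or two exploratory tables on data already collected. Cells will be sparse: about 100 participants over four arms and three categories is 100 / 12, or roughly 8 per cell, even if use were evenly spread and nobody dropped out. The overall table should therefore carry the interpretation, with the by-treatment split as description only.

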8.4.7 Extent of exposure

8.4.7.1 Treatment duration

Duration of treatment (in months) will be categorised in intervals (0-1, 1-3, 3-5, 5-7, 7-9, 9-11 >11) and summarised descriptively by treatment regimen on the Safety population.

Study drug exposure (in months) will be summarised by treatment group on the Safety population using descriptive statistics.

8.4.7.2 Treatment compliance

The number of subjects with infusion interruptions and incomplete infusions will be summarised at each month and overall.

8.5 Efficacy analyses

This section addresses separately the analyses to be conducted on the primary, secondary and exploratory efficacy variables. Analyses for the primary efficacy endpoints and selected secondary endpoints will be analysed on the FAS, mFAS, the Non-restricted FAS and the per-protocol populations, while analyses for the remaining secondary and exploratory efficacy endpoints will be analysed on the FAS population only.

All definitions relative to efficacy and exploratory endpoints are detailed in [Section 7.1.3](#).

8.5.1 Analysis methods

For all continuous outcomes, where appropriate, an ANCOVA model analysis will be performed. Analyses will include the fixed, categorical effects of treatment and randomisation stratum as well as the associated baseline value as a covariate. Significance tests for treatment differences (between Setrusumab doses) will be based on least-squares means (LSMeans).

ANCOVA analyses dealing with nested observations within a patient (e.g., vertebral assessments) will consider this relationship in the modelling by specifying patient as a random factor.

If the input data is log-transformed then LSMean and LSMeans differences between treatment groups will be back-transformed to their original scale for descriptive purposes. After subtracting the geometric mean of the log baseline values, the back-transformed LSMeans will correspond to the percentage change from baseline, while the back-transformed LSMeans differences will correspond to the ratio of percentage changes from baseline.

Time to event variables (e.g., time to first fracture) will be analysed using Kaplan-Meier methods, and quartiles for the median time to event will be presented together with their 95% confidence intervals.

Count variables (e.g number of new fractures) will be analysed using Poisson regression. Analyses will include treatment and randomisation as fixed effects and the logarithm of the duration of exposure to study medication will be included as an offset variable in the model. In case over dispersion is a concern, the negative-binomial regression model will be applied instead.

For binary outcomes the proportion of patients with a response will be summarised and compared between treatment groups using Chi squared test.

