7.1.3.2 Vertebral fracture assessments

The lateral spine radiographs will be assessed for vertebral fractures using the Genant Semiquantitative Scoring Method assigning each vertebra a grade between 0 and 3 (SQ score):

- Grade 0: normal
- Grade 1: mild fracture
- Grade 2: moderate fracture
- Grade 3: severe fracture

A new vertebral fracture is defined as an SQ score ≥ 1 at a post baseline visit where the baseline SQ score = 0 for the associated vertebrae. A subject is defined as having a new fracture at a visit if they have at least 1 vertebra with a new fracture.

A worsening vertebral fracture is defined as an increase in SQ score ≥ 1 from the previous visit (where the baseline SQ score > 0) for the associated vertebrae. A subject is defined as having a worsening fracture at a visit if they have at least 1 vertebra with a worsening fracture.

The sum of all grades at a visit is defined as sum of all SQ scores across all vertebrae assessed at a visit by the Genant Semiquantitative Scoring Method.

The below vertebral height parameters (for each vertebra) will be derived from the 6-point vertebral morphometry assessments:

- Anterior /Posterior height ratio (HA/HP)
- Mid / Posterior height ratio (HM/HP)

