8.5.3.3.1 Vertebral Fractures

For all vertebral assessments the X-ray scans will be used as source.

The number and proportion of patients with a new vertebral fracture and new or worsening vertebral fracture will be summarised by treatment group throughout the treatment period (at each visit). In addition, a P-value for the comparison between each group will be provided using a Chi squared test.

The total number of new vertebral fractures and new or worsening vertebral fractures per patient during the treatment period will be compared between each treatment group using a poisson regression model as described in section 8.5.1. An estimate of the ratio of new vertebral fractures and new or worsening vertebral fractures between treatment groups will be presented together with a two-sided 95% confidence interval and P-value.

For patients that have a vertebral fracture a shift table of the change in fracture grade will be presented. The number and percentage of patients with each level of change (from worst baseline grade to worst post-baseline grade) will be displayed.

Finally the total sum of vertebral fracture grades will also be analysed via ANCOVA in the same manner as the change from baseline in Tr.vBMD (radius) on HRpQCT (see Section 8.5.2.1).

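### The count model for new and for new-or-worsening vertebral fractures omits the baseline vertebral fracture count, a covariate already collected that may, but need not, improve precision

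*SAP*

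**What the plan says.** SAP 8.5.1 sets the general method: "Count variables (e.g number of new fractures) will be analysed using Poisson regression". On the terms it says "Analyses will include treatment and randomisation as fixed effects"; I read the second as the OI-type stratum, which the ANCOVA paragraph of the same section names. On follow-up time, "the logarithm of the duration of exposure to study medication will be included as an offset variable in the model". On excess variation, "In case over dispersion is a concern, the negative-binomial regression model will be applied instead".

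SAP 8.5.3.3.1 takes the number of new, and of new or worsening, vertebral fractures per patient, which "will be compared between each treatment group using a poisson regression model as described in section 8.5.1". It adds no term. Protocol 11.3.1 lists the Poisson regression, if appropriate, and names no covariates. I found no other section that adds a baseline term.

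Two further texts bear on the point. SAP 7.1.3.2 says "A new vertebral fracture is defined as an SQ score ≥ 1 at a post baseline visit where the baseline SQ score = 0", and a worsening fracture requires a baseline grade above 0. For continuous outcomes, the ANCOVA in SAP 8.5.1 has treatment and stratum "as well as the associated baseline value as a covariate".

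**The concern.** The baseline grade of every readable vertebra is available from the screening radiograph (Protocol Schedule of Activities and 10.1.1.3), so the covariate needs no new data. OI type is a coarse substitute: it has two levels, with Types III and IV combined. Inclusion criterion 3 accepts long-bone, rib, hand or foot, or vertebral fractures, so participants with no vertebral fracture and with many can share a stratum.

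If the baseline count predicts the outcome within stratum, leaving it out sends that variation into over-dispersion. The effective interval for the rate ratio is then wider than it needs to be, or a plain Poisson standard error is too small. With 25 per arm, chance differences in baseline count would also add noise to the comparison. What is at stake is efficiency in a secondary analysis.

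**Working it through.** **Inputs from the documents.** 25 per blinded arm (SAP 5); two-sided 5% tests (SAP 8.1.4); two strata (SAP 3.2.1); model terms as above. No fracture rate, baseline count, dispersion or power is given for this endpoint, so there is no stated figure to reproduce. All other inputs below are assumptions.

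**Step 1, formula.** Let mu be the mean count per patient and CV² the within-stratum squared coefficient of variation of patients' true rates. The variance of an arm's log rate is (1/mu + CV²)/n unadjusted, and (1/mu)/n if a covariate explains all that variation. The inflation from omission is at most 1 + mu × CV².

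| mu | CV² = 0.07 | CV² = 0.5 |
|---|---|---|
| 0.5 | 1.04 | 1.25 |
| 1 | 1.07 | 1.50 |
| 2 | 1.14 | 2.00 |

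**Step 2, direction.** Two effects pull against each other. More baseline fractures leave fewer vertebrae that can have a new one, which lowers the count. Greater fragility, if present, raises it. The documents support the first by definition and give nothing on the second.

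**Step 3, variance simulation.** Three arms of 25, 400 runs in each of 24 scenarios. Assumed: 13 readable vertebrae, 60% Type I, 25% or 40% of vertebrae fractured at baseline, mu of 0.5, 1 or 2, rate ratio 0.5, per-vertebra risk multiplied by exp(0), exp(0.1), exp(0.2) or exp(0.3) per baseline fracture. The table gives the variance of the log rate ratio under the SAP model, divided by that with the baseline count as covariate and log(vertebrae at risk) in the offset.

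| Case | Variance ratio |
|---|---|
| All scenarios | 0.96 to 1.25 |
| At-risk limit alone, exp(0) | 0.96 to 1.13 |
| Effects largely offsetting, exp(0.1) or exp(0.2) | 0.98 to 1.06 |
| All scenarios with mu = 0.5 | 0.96 to 1.09 |

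The largest ratio means a standard deviation √1.25 = 1.12 times as large. With the count as covariate and no change of offset, the scenario with the largest gain (mu = 2, 25%, exp(0.3)) gives (0.266/0.247)² = 1.16.

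The standard error printed by the plain Poisson model hardly moves (for example 0.357 against 0.359), and its power stays within about 3 points. That alone does not show the omission to be harmless. Residual dispersion was 1.01 to 1.42 without adjustment and about 1.0 with it, and a plain Poisson standard error ignores dispersion. At dispersion 1.42 the effective critical value is 1.96/√1.42 = 1.645, so a nominal 5% test would run near 10% unless the negative-binomial switch is made.

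**Step 4, power with a dispersion-corrected Poisson test.** 25 per arm, rate ratio 0.4, covariate log(1 + baseline count), 600 or 800 runs. Power in % without and with the covariate, at mean counts of 0.5, 1.0 and 1.5:

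| Assumed mechanism | 0.5 | 1.0 | 1.5 |
|---|---|---|---|
| Rising risk, log-rate slope 0.4, no at-risk limit | 37.3, 36.7 | 68.8, 69.0 | 83.5, 85.5 |
| Rising risk, slope 0.8, no at-risk limit | 34.7, 36.5 | 62.7, 67.8 | 71.8, 84.2 |
| Same, repeat run | 30, 34 | 58, 66 | 72, 84 |
| At-risk limit alone | 36, 36 | 64, 66 | 83, 85 |
| Both together | 35, 35 | 68, 69 | 82, 85 |

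A further run of the at-risk limit alone gave changes of -2 to 0 points. The last two rows and that run together give -2 to +3 points. The slope 0.8 rows give about +2 (36.5 - 34.7 = 1.8) to +12 (84.2 - 71.8 = 12.4). A slope of 1.2 gave larger gains, up to 84.7 - 56.3 = 28 points, but it is a steep assumption with no at-risk limit and I place no weight on it. The Monte Carlo standard error of one power figure is at most √(0.25/600) = 2.0 points, so the small changes cannot be told from zero. In the 600-run set, type I error stayed near 5% with and without the covariate.

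**The case against.** The strongest objection is that the definition of a new fracture does not deliver the gain. A reader might infer that, because a new fracture counts only "where the baseline SQ score = 0 for the associated vertebrae", the omission must cost precision. It need not: the at-risk limit alone yields roughly nothing, and gains of several points appear only if prior fractures raise later risk, which the documents do not state. This stands, and it is why the gain is put conditionally.

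The at-risk argument also fails for new-or-worsening counts. A grade 0 vertebra can fracture and a grade 1 or 2 vertebra can worsen, so only grade 3 vertebrae drop out. This stands; for that count the case rests on prognosis alone.

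A reader might also see an inconsistency with the ANCOVA models. There is none: a count of new fractures is zero for everyone at baseline, so it has no baseline value of its own to carry over.

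The SAP already allows a negative-binomial model and analyses the sum of grades with baseline adjustment. Both are true. However, the switch has no stated criterion and absorbs the variation without explaining it. The sum of grades is a different outcome. Protocol 11.3.1 also plans a baseline-adjusted ANCOVA of the percent change in number of vertebral fractures, but SAP 8.5.3.3.1 does not carry it over.

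Lastly, one could say that log(vertebrae at risk) in the offset is the direct remedy. That suits new fractures only, and it is undefined for a patient with no grade 0 vertebra. A covariate whose sign is free serves both counts.

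**Conclusion.** The omission is confirmed from the text. Its cost is not established. Under the assumptions above, adding the covariate changes power by about -2 to +3 points if the baseline count acts only through vertebrae at risk or if the two effects cancel, and by about 2 to 12 points if more baseline fractures clearly raise later risk. The assumed rate ratios (0.4 and 0.5) are between active doses, and no document supports them.

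A reader might infer a biased comparison. The documents do not support that: randomisation prevents systematic bias, and chance imbalance is part of the ordinary sampling error. The analysis is secondary, one of several on vertebral outcomes, with no multiplicity adjustment. The primary Tr. vBMD test and the dose-response analysis do not use it. This is a minor improvement worth making because it is cheap.

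**What to change.** Before unblinding, in SAP 8.5.1 and 8.5.3.3.1, add log(1 + number of vertebrae with SQ of 1 or more at baseline) as a pre-specified covariate in the Poisson and negative-binomial models for both counts, beside treatment and OI-type stratum and with the exposure offset unchanged. State that the present model is used only if the adjusted model does not converge, so that the choice cannot depend on the treatment result.

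The cost is one SAP line and one model term, with no new data and no conflict with the protocol. The downside is one more parameter when events are few, which is also where the gain is likely to be smallest and non-convergence most likely.
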